# Stryker®

# Tritanium® Primary Acetabular Shell LOWER EXTREMITY ACTIVITY SCALE (LEAS)

	AL INFORMAT	ON				Party of
S	SUBJECT INI	TIALS:	VISIT DATE:	VISIT:	SUBJECT ID:	
			(DD MMM NOOO)			
. LOW	ER EXTREMITY	ACTIVITY SCALE	(DD-MMM-YYYY)			NASAU.
		Enter da	ata as completed b	y the subject per par	er questionnaire.	
1. (	) I am con	fined to bed al	l day.			
2. (	) I am con	fined to bed m	ost of the day excep	t for minimal transfer a	ctivities (going to the bathroom,	etc.).
3.	) I am eith	er in bed or sit	ting most of the day			
4. (	) I sit mos	of the day, ex	cept for minimal tra	nsfer activities, no walk	ing or standing.	
5. (				•	nount in my house. (I may rarely chair or scooter for transportation	
6. (			e to a moderate degi for an appointment.		house on a regular basis. (I may	leave
7.	) I walk ar	ound my house	e and go outside at v	vill, walking one or two	blocks at a time.	
8.		ound my house permitting).	e, go outside at will a	and walk several blocks	at a time without any assistance	
9. (		and about at w permitting).	ill in my house and c	an go out and walk as n	nuch as I would like with no rest	rictions
10.	I am up a	and about at w	ill inside my house a	nd outside. I also work	outside the house in a:	
	() m	inimally active	job O mo	derately active job	

extremely active job

	
11.		and about at w		nd outside. I also partic	ipate in relaxed physical activity	such a
		ccasionally 2-3 times per m		times per week	O daily	
12.		and about at w competitive lev		nd outside. I also partic	ipate in vigorous physical activit	У
		ccasionally 2-3 times per m		times per week	O daily	
I. COM	IMENTS					
I. COM						ß,

## Stryker ®

# Tritanium® Primary Acetabular Shell NOTICE OF PROTOCOL DEVIATION

Orthopaedics

	CURIECT INITIALS.
	SUBJECT INITIALS: DATE OF DEVIATION: SUBJECT ID:
	(DD-MMM-YYYY)
DEVIAT	TION INFORMATION
. TYPE	OF DEVIATION
0	Informed Consent:  Study procedures performed prior to informed consent Incorrect informed consent version used Other
0	Inclusion / Exclusion: Subject enrolled does not meet the Inclusion / Exclusion criteria
0	
0	Treatment: Protocol specified study component(s) not implanted (Check all that apply)  Acetabular Shell* Acetabular Liner Acetabular Insert Femoral Bearing Head Femoral Steres Complete Study Termination form
0	Evaluation(s): (Specify one visit below)
	VISIT: O O O O O O O O O O O O O O O O O O O
	Missed entire visit (Select if entire visit did not occur; no CRF and X-ray completed)  For a missed visit, record the day after visit interval window closure.
	Deviation in visit (Check all that apply and specify)  Required form(s)/X-ray(s) not done  [ EQ-5D  Follow-up Questionnaire
	Evaluation(s) occurred outside of protocol specified time window Functional Evaluation  LEAS
	Unevaluable X-ray (i.e. unreadable/poor quality)
0	Adverse Event: Protocol-specific Adverse Event reporting criteria not met - AE reported to Sponsor X-ray - A/P Femur
0	after 24 hours of knowledge of event. X-ray - Lateral
0	Other:
Briefl	y describe the deviation and why this occurred.
OMMEN	NTS The state of t

Stryker®

## Tritanium® Primary Acetabular Shell POST-OP FUNCTIONAL EVALUATION

Orth	nopaedics
------	-----------

A. PAIN		(DD-MM	M-YYYY)	VISIT	SUBJECT	DENTIFIER:	
PAIN O	None or ignores it						
	None, or ignores it						
O	Slight, occasional, n	o compromise in	activities				
0				oderate pain with unusual activity,			
0	Moderate pain, tole May require occasion			ons to pain. Some limitations of ord ger than aspirin	dinary activity or wor	·k.	
0	Marked pain, seriou	s limitation of act	ivities				
0	Totally disabled, crip	ppled, pain in bed	, bedridd	len			
I. FUNCTION	N / GAIT				Kiel Market		
B. LIMP		C. SUP	PORT		D. DISTAN	CE WALKED	
O None		○ No	ne		O Unlimit	ed	
○ Slight		○ Car	ne, long v	walks	O Six bloc	ks	
O Moder	rate	O Car	ne, most	of the time	O Two or three blocks		
O Severe or unable to walk		O On	One crutch			O Indoors only	
0	Swiffer to the Cartes		○ Two canes			Bed and chair only	
	ONAL ACTIVITIES			es, walker or unable to walk	O Bed and	d chair only	
	ONAL ACTIVITIES		o crutche	es, walker or unable to walk  G. SITTING		C TRANSPORTATIO	
II. FUNCTIO		O Tw	o crutche	G. SITTING	H. PUBLI	C TRANSPORTATIO	
II. FUNCTIO  E. STAIRS  Normally	without using a rail	F. SOCKS / SHO	o crutche		H. PUBLI	C TRANSPORTATIO	
II. FUNCTIO  E. STAIRS  Normally	without using a rail using a rail	F. SOCKS / SHO	o crutche	G. SITTING  Any chair, 1 hour	H. PUBLI  Able to	C TRANSPORTATIO	
III. FUNCTIO  E. STAIRS  Normally  Normally  In any ma	without using a rail using a rail	F. SOCKS / SHO	o crutche	G. SITTING  Any chair, 1 hour  High chair, 1/2 hour	H. PUBLI  Able to	C TRANSPORTATIO	
II. FUNCTIO  E. STAIRS  Normally  Normally  In any ma  Unable to	without using a rail using a railing anner	F. SOCKS / SHO  With ease  With difficul  Unable	OES	G. SITTING  Any chair, 1 hour  High chair, 1/2 hour	H. PUBLI  Able t  Not all	C TRANSPORTATION o use ble to use	
III. FUNCTION  E. STAIRS  Normally  Normally  In any ma  Unable to	without using a rail using a railing anner o use stairs	F. SOCKS / SHO  With ease  With difficul  Unable	OES	G. SITTING  Any chair, 1 hour  High chair, 1/2 hour  Unable to sit comfortably in	H. PUBLI  Able t  Not all any chair	C TRANSPORTATION o use ble to use	
II. FUNCTIO  E. STAIRS  Normally  Normally  In any ma  Unable to  ABSENCE O	without using a rail using a railing anner o use stairs  OF DEFORMITY (or contracture < 30°	F. SOCKS / SHO  With ease  With difficul  Unable	OES Ity	G. SITTING  Any chair, 1 hour  High chair, 1/2 hour  Unable to sit comfortably in	H. PUBLI  Able t  Not all any chair	C TRANSPORTATION o use ble to use	
E. STAIRS  Normally  Normally  In any ma  Unable to  ABSENCE Contact of the conta	without using a rail using a railing anner o use stairs  OF DEFORMITY (or contracture < 30°	F. SOCKS / SHO  With ease  With difficul  Unable	OES  Ity	G. SITTING  Any chair, 1 hour  High chair, 1/2 hour  Unable to sit comfortably in a  J. RANGE OF MOTIO	H. PUBLI  Able t  Not all any chair	C TRANSPORTATION o use ole to use	
E. STAIRS  Normally  Normally  In any ma  Unable to  ABSENCE Contact of the conta	without using a rail using a railing anner ouse stairs  OF DEFORMITY (or contracture < 30° ion < 10°	F. SOCKS / SHO  With ease  With difficul  Unable  perative side only) Ye	OES No	G. SITTING  Any chair, 1 hour  High chair, 1/2 hour  Unable to sit comfortably in a  J. RANGE OF MOTIO  Permanent (Fixed) Flexion to	H. PUBLI  Able t  Not all any chair	C TRANSPORTATION o use ole to use	
E. STAIRS  Normally  Normally  In any ma  Unable to  ABSENCE C  Fixed flexion of the control  Fixed adduction of the control  Fixed internal	without using a rail using a railing anner o use stairs  OF DEFORMITY (or contracture < 30° ion < 10° I rotation in extension	F. SOCKS / SHO  With ease  With difficul  Unable  perative side only) Ye	OES No	G. SITTING  Any chair, 1 hour  High chair, 1/2 hour  Unable to sit comfortably in a  J. RANGE OF MOTIO  Permanent (Fixed) Flexion to  Abduction to	H. PUBLI Able t Not all any chair  (Operative side only	C TRANSPORTATION o use ole to use	

08Feb2010

## Stryker® Orthopaedics

## Tritanium® Primary Acetabular Shell POST-OP FUNCTIONAL EVALUATION

IV.	EVENTS	

K. Have there been any protocol defined Adverse Events since the last visit?	Yes*	No lete an AE form for each.
USE THIS SECTION TO REPORT MEDICAL EVENTS OTHER THAN PROTOCOL DEFIN	ED ADVERSE	EVENTS.
L. Has the subject seen a doctor for any medical event since the last visit?  *If Yes, specify:	○ Yes*	○ No
M. Has the subject been hospitalized for any elective surgery since the last visit	? ∩ Yes*	○ No
*If Yes, specify (check all that apply)		
*Provide Details		
N. Is anything currently affecting the subject's function? Yes* No *If Yes, specify:		
. COMMENTS		
Reason for Save Verification / Confirmation Method		

Stryker®

## Tritanium® Primary Acetabular Shell PRE-OP FUNCTIONAL EVALUATION

|--|

Moderate pain, tole May require occasio Marked pain, seriou	verage activities, ran erable but makes con onal pain medication as limitation of activit	ivities ely mo cessio stron cies	oderate pain with unusual activity, ons to pain. Some limitations of or ger than aspirin	
Totally disabled, crip II. FUNCTION / GAIT	opled, pain in bed, b	edrido	den	
B. LIMP	C. SUPPO	ORT		D. DISTANCE WALKED
○ None	○ None			○ Unlimited
○ Slight	O Cane,	long	walks	○ Six blocks
○ Moderate	Cane,	most	of the time	Two or three blocks
O Severe or unable to walk	One c	rutch		O Indoors only
	O Two o			Bed and chair only
	O Two c	rutch	es, walker or unable to walk	
III. FUNCTIONAL ACTIVITIES  E. STAIRS	F. SOCKS / SHOE	S	G. SITTING	H. PUBLIC TRANSPORTATION
Normally without using a rail	○ With ease		Any chair, 1 hour	
Normally using a railing	With ease  With difficulty		High chair, 1/2 hour	Able to use  Not able to use
In any manner	O Unable		Unable to sit comfortably in any chair	
Unable to use stairs	Ollable		O onable to sit conflortably in	any chair
I. ABSENCE OF DEFORMITY (O	perative side only) Yes	No	J. RANGE OF MOTIO	
Fixed flexion contracture < 30°	0	0	Permanent (Fixed) Flo	exion
Fixed adduction < 10°	0	0	Flexion to	
Fixed internal rotation in extension	n < 10°	0	Abduction to	
Leg length discrepancy less than 3	.2 cm	0	Adduction to	°
	(Specify)	cm	External Rotation in E	Extension to °
			Internal Rotation in E	xtension to °
Before proceeding to the r If changing any HHS data f				te HHS
IV. COMMENTS				COG POSICIONES INSCRIBINATION
Reaso Verification / Confirmation	n for Save			

30Apr2010

## Stryker®

## Tritanium® Primary Acetabular Shell

Orthopaedics

## SURGICAL DETAILS

Submit Surgical Details CRF ONLY if surgery is performed and subject receives study device.

GENERAL INFORMATION					
SUBJECT	INITIALS:	SURG	GERY DATE:	SUBJECT ID:	
	The state of the s				
I SUBCICAL DETAILS		(DC	D-MMM-YYYY)		S. St. Phys.
I. SURGICAL DETAILS	D. MALICOLE I	DEDAID OD			
A. APPROACH  Anterior	B. MUSCLE I		REATTACHMENT REQUIR		TION USED?
Anterolateral	O No		which muscle group?	○ Yes	
O Posterior/ Posterola		A CHARLES TO COL	rnal Rotators eus Medius	○ No	
O Dual Incision	iteral	Othe	and the state of t		
() Lateral		_ othe			
D. INCISION LENGTH					
	E. DURATIO			F. ESTIMA	TED BLOOD LOSS
cm	Skin to Ski	n	minutes		cc
I. PROSTHESES					
G. PROSTHESES - Upload a copy of the con	nnonent lahel/s) implant	her	H. OTHER?	O Yes* O N	No
Acetabular Shell -	inponent tabel(s) implant		*If Yes, specify an	d upload a copy of the la	bel(s).
Go to Subject Informatio	n screen and enter data	in Products	tab. Add Row Other (S	Specify) Reference #	Lot#
	Reference #	Lot#	Reset	Specify) Reference #	LOT#
Acetabular Liner		II Nowe	×		
Acetabular Insert	Reference #	Lot#	Attitude (S.V.)	NAME OF TAXABLE PARTY.	
Acctabalal Insert	Reference #	Lot#			
Femoral Bearing Head	- HOIGIGING II	2001			
	Reference #	Lot#			
Femoral Stem					
I. BONE SCREWS USED?	○ Yes* ○ No				
*If Yes, specify and uploa					
Add Pow					
Reset	e# Lot:	#	J. INTRAOPERATIVE	COMPLICATION?	
X				E form. (a) Yes* (	No
				0	
			K. DISCHARGED TO:	: (Check One)	
			Skilled Nursing Fa	cility	
			Chronic Care Cent	ter	
			Rehabilitation Un	it	
			O Home		
			the Electric transfer of the second		
			Other: (Specify)		
			Discharge Date:		
I. COMMENTS				DD-MMM-YYYY	
II. COMMENTS					
	Reason for Save				
Verification / Cor	nfirmation Method				
			Cubacia		
0Aug2011 Ver 1 0			Submit		
9Aug2011 Ver.1.0		Pa	age 1 of 1		

[figure not shown]

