#### 9.4.2 Sample Size Calculation

A literature review shows that at 5 years of follow-up there is a 97.9% to 99.6% success rate in similar devices using revision or removal of the acetabular component as the defining factor. Based on these results, it should be a reasonable assumption that the base success rate of revision or removal of the Tritanium® Acetabular Shell will be approximately 99% at 5 years. Using a base success rate of 99% from the literature and a delta of 5%, it was calculated that 142 total cases implanted with the Tritanium® Acetabular Shell would be needed to prove non-inferiority with 95% power. With a minimum of 142 cases analyzed, the primary hypothesis of the study will be met if the lower bound of the 90% confidence interval for the 5-year success rate is greater than 94%. By factoring in a 20% lost to follow-up rate within a 5-year period, the required sample size increases to 177 cases. Cases will continue to be enrolled until a total of 240 cases are implanted with the Tritanium® Acetabular Shell; half of these cases will use the X3® polyethylene insert alone as the bearing surface and the other half will use the MDM™ liner coupled with a compatible ADM/MDM™ X3® insert as the bearing surface.

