# **9.4.3 Interim Analyses and early Stopping Considerations** No interim analysis is planned.

### 9.4.4 Efficacy Patient Populations

### 9.4.4.1 **Efficacy**

#### Per protocol population:

The study population for analysis will include all subjects who receive the Tritanium® Acetabular Shell. This does not include cases censored from analysis or cases that are unavailable for evaluation at the 5-year primary endpoint.

The primary and secondary efficacy analyses will be based on the per protocol population.

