### 9.4.4.2 Safety

#### **Safety Population:**

The safety population will include all non-censored subjects who received the Tritanium® Acetabular Shell.

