### Termination Reason Date of Termination

Death Date of death

Investigative center termination Date of study close-out visit

Lost to follow-up Date Stryker termination approval given

Voluntary withdrawal Date subject notified center of withdrawal

Revision/removal of study device Date of revision/removal procedure

Study device not implanted

Surgery not performed

Date of surgery

Date Stryker termination approval given

At the time of study surgery it is required that the following components are implanted:

- Tritanium® Acetabular Shell
- Stryker X3® polyethylene inserts (120 cases)
- Stryker MDMTM liners with ADM/MDMTM X3® polyethylene inserts (120 cases)
- Stryker LFIT™ CoCr heads, BIOLOX *delta* or alumina ceramic heads
- Stryker Universal Adapter Sleeves (for use with BIOLOX delta universal ceramic heads)
- Compatible Stryker femoral stems
- Stryker Orthopaedics Torx Bone Screws

Revision or removal of the Tritanium® Acetabular Shell constitutes a failure and study termination for the subject.

If MDMTM liner, acetabular insert (either X3® or ADM/MDMTM X3®) or femoral head exchange is required during the study, the event is considered a reoperation and does not constitute a failure or study termination.

If femoral stem revision is required during the study, the event is considered a reoperation and does not constitute a failure or study termination.

If the subject fails to return for his/her follow-up appointments, every effort should be made to contact the subject to assess his/her health status. If after attempting to contact the subject through three documented phone calls and a certified letter, the subject still does not respond, he/she will be considered lost to follow-up. A Study Termination eCRF will be completed only after notifying Stryker of the subject's status and being given approval to terminate.

In the event a subject does not have surgery, Stryker should be contacted to discuss if/when the surgery will be rescheduled. If the surgery is rescheduled more than 4 months from the date of preoperative data collection, the subject will need to be re-consented, all preoperative data will need to be re-collected and all original preoperative data will need to be removed from the database. If the surgery is not to be rescheduled or if the subject is no longer considered an

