Intraoperative fissure, fracture, or perforation of the femur, acetabulum or trochanter can occur due to impaction of the component into the prepared femoral canal or acetabulum. Postoperative femoral or acetabular fracture can occur due to trauma, the presence of defects or poor bone stock.

If bone screws are used, appropriate selection of bone screw length and location is essential to avoid damage to underlying soft tissue structures. Perforation of the pelvic wall can result in internal bleeding and possible damage to vital organs.

Metal sensitivity reactions have been reported following joint replacement.

AEs may necessitate reoperation, revision, arthrodesis of the involved joint, girdlestone or amputation of the limb.

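### The safety population leaves out subjects in whom the Tritanium shell was attempted but not left in place, so adverse event rates can understate intraoperative harm

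*Combined protocol and SAP*

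**What the plan says.** All three analysis populations depend on receipt of the shell. For efficacy, Section 9.4.4.1 begins "The study population for analysis will include all subjects who receive the" (the Tritanium shell). For safety, Section 9.4.4.2 reads "The safety population will include all non-censored subjects who received the Tritanium® Acetabular Shell". Section 9.4.4.3 sets the same condition for the survival analysis. Enrollment continues until 240 hips are implanted (Sections 3.3 and 9.4.2), so a hip finished with another cup is replaced.

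Section 10.3 lists "Study device not implanted" as a termination reason. Taking the two columns of that list in order, the termination date is the date of surgery.

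The Surgical Details form (Appendix E) holds the intraoperative complication item, which calls for an AE form when answered yes. Its header instruction is "Submit Surgical Details CRF ONLY if surgery is performed and subject receives study device".

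Other provisions keep such a subject's harms in view. Section 8.1 makes protocol-defined AEs reportable from consent. The AE form has an intraoperative option and a box for acetabular crack or fracture. Section 9.2.2 says every AE will be listed and tabulated, with percentages and 95% confidence intervals.

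**The concern.** The protocol treats injury during impaction as a known risk. Section 12.2 says "Intraoperative fissure, fracture, or perforation of the femur, acetabulum or trochanter can occur due to impaction of the component" into the prepared bone. An acetabular fracture, or a shell that will not seat, is also a plausible reason for a surgeon to finish with a different cup. Such a hip would carry relevant safety information about the device at surgery, yet on a plain reading it lies outside the denominator for AE rates, and the form that would prompt its AE report is not submitted.

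What is at stake is the intraoperative part of the AE rates, which Section 2.2 compares with the historical control and with published data. If events are more frequent in attempted-but-not-kept hips than in kept hips, the omission lowers those rates.

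**Working it through.** **1. The plan's own figures.** Section 9.4.2 gives 142 analyzed cases as "needed to prove non-inferiority with 95% power", with 99% expected success, a 94% limit and the lower bound of a 90% confidence interval. With an exact binomial (Clopper-Pearson) bound, 142 hips pass with at most 3 failures, and power at 99% is 94.5%. Inflation for 20% loss is 142 / 0.8 = 177.5, against the stated 177. Both figures reproduce. They concern implanted hips and do not depend on this point. The plan states no figure for abandoned attempts.

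**2. Following one subject through the plan.** Take a consented subject in whom the shell is attempted and another cup is left in place.

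| Place | Effect on this subject |
|---|---|
| 9.4.4.1, 9.4.4.2, 9.4.4.3 | In none of the populations, unless the attempt counts as receipt |
| 10.3 | Terminated, dated to surgery |
| 8.1 | Intraoperative AE still reportable, because reporting starts at consent |
| 8.1, 8.4 | Each event followed until it resolves or stabilizes, or the study ends |
| 9.2.2 | All AEs tabulated, as number and percent |
| 11.6 and the deviation form | Non-implantation recorded, with the reason |
| 9.4.4.4 | Reported separately if the deviation could affect outcome |

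Two pairs do not fit together. Section 9.2.2 counts all AEs, while 9.4.4.2 supplies a denominator without this subject. Section 10.3 ends participation on the day of surgery, while 8.1 and 8.4 require the event to be followed further.

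**3. Which form prompts the AE report.**
- Surgical Details has the prompt but is not submitted.
- The Study Termination form asks for an AE form on the death and revision/removal lines. On the not-implanted line it asks for a reason and a Protocol Deviation form only.
- The Post-Op Functional Evaluation asks about AEs, but a terminated subject has no further scheduled visit.

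The duty to report stands, but no surgery or termination form brings it up.

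**4. Size.** The abandonment proportion a is not in the documents. As an assumption, take 0.5% to 3% of attempts. Reaching 240 implanted hips then takes 240 / (1 - a) attempts, of which 240a / (1 - a) are abandoned.

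| a (assumed) | Abandoned hips |
|---|---|
| 0.5% | 240 × 0.005 / 0.995 = 1.2 |
| 1% | 240 × 0.01 / 0.99 = 2.4 |
| 2% | 240 × 0.02 / 0.98 = 4.9 |
| 3% | 240 × 0.03 / 0.97 = 7.4 |

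Let r be the event rate in kept hips and q the rate in abandoned ones. The rate over all attempts is (1 - a)r + aq, so reporting r alone is too low by a(q - r). That cannot exceed a, and it is zero if q = r.

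**The case against.** The strongest reply is that the plan does not lose these harms, and for collection that is right. Reporting runs from consent, and investigators must ask about AEs at each contact. The AE form is separate from Surgical Details. Device-related or uncertain events go to the sponsor within 24 hours (Section 8.3), and removed Stryker components are retrieved (Section 6.2). Non-implantation and its reason are recorded on two forms. A reader might infer that intraoperative harms vanish or that follow-up of an event stops at surgery; the documents do not support either. What survives is the denominator, the missing prompt and the unreconciled termination date. Section 9.4.4.4 covers only part of this: it is conditional, names no table, and itself removes the case from the safety population.

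The scenario is also inferred. The plan never describes a shell that is tried and abandoned, and does not define receipt for it. Such a shell could be read as received and then removed, which would make it a primary failure under Section 9.1.4. That objection stands, and it is a reason to define the term.

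Three stronger readings are tempting and should not be made:
- A reader might infer that the rule works like a run-in, keeping only shells that fixed. The condition is implantation, not fixation. Hips with poor fixation, early loosening or an intraoperative fracture stay in if the shell was kept.
- A reader might infer that screw usage is biased. The synopsis defines that measure as screw use in Tritanium cluster hole procedures, and a shell that was not kept has no natural value for it.
- A reader might recompute the 5-year rate with abandoned hips as failures: with an assumed 2 revisions in 192 evaluable hips (240 × 0.8), adding 5 failures takes the exact lower bound from 96.8% to 93.4%, below 94%. That uses an invented count, treats every abandonment as a device failure, and changes the endpoint. The plan's endpoint is revision or removal of the acetabular component, and restricting it to implanted hips is reasonable.

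**Conclusion.** The point holds for the safety analysis. On a plain reading, attempted-but-not-kept hips lie outside the population for AE rates, no surgery or termination form prompts their AE report, and the plan does not reconcile this with its statement that all AEs are tabulated. The rates can understate intraoperative acetabular fracture and failed seating. The shortfall is at most the abandonment proportion itself, which the documents do not give: 0.5 to 3 percentage points, or about 1 to 7 hips, under the assumed range.

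This rests on two assumptions: that receipt means the shell was left in place, and that events are more common in abandoned attempts than in kept hips. The sample size and the primary analysis are unaffected if implanted hips remain the basis. This is an inexpensive improvement to safety reporting and does not undermine the primary conclusion.

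**What to change.** - In Section 9.4.4.2, define the safety population as all consented subjects in whom implantation of the Tritanium shell was attempted.
- State whether a shell removed in the same operation counts as received, or as a removal under Section 9.1.4.
- Lift the restriction on the Surgical Details form so that it is required for every attempted case, with an AE form if an event occurred.
- Add the AE prompt to the not-implanted line of the Study Termination form.
- Reconcile the termination date in Section 10.3 with the AE follow-up rules in Sections 8.1 and 8.4.
- Tabulate the number of attempted-but-not-implanted hips and the reasons, from the deviation and termination forms, beside the AE and 5-year results.
- Keep the primary rate on implanted hips.

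The cost is one definition, two form changes, a few extra forms and a slightly less favorable intraoperative AE rate. If enrollment has closed, counts and reasons should be recoverable from the deviation and termination forms, and surgical details from the operative notes that Section 7.2 already names as a source.
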